5.6 Description of Treatment and Definition of Exposure to trial medication

Not applicable as there will be no use of any trial medication. Subjects’ embryos will be observed using morphological assessments as standard of practice at the IVF laboratories and a part of the trial patients in an allocation ratio of 2:1 will be assigned to have EEVA Time Lapse system embryos observation and assessments added to their standard assessment. Culture conditions and elements will be the same for all embryos in the laboratory regardless of their allocation at randomization.

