6.3.2 Oocyte Retrieval, Insemination, and Day 1 Fertilization Check

Oocyte retrieval and insemination will follow the standard protocol in place at each trial site. Data will be recorded on the **Oocyte Retrieval and Insemination/Fertilization** eCRF including:

- Date and time of oocyte retrieval
- Number of oocytes retrieved
- Andrology information
- Insemination method
- Total number of normally fertilized eggs (2PN)
- Culture conditions (including gas phase, media, and protein, etc.)
- Embryo morphological grading may be assessed on Day 2 as per local laboratory standard practice in those subjects randomized to the Morphology group only.

6.3.3 Embryo Day 3

Day 3 embryo morphological grading will be performed according to standard protocol and laboratory procedure manual. Eeva results will be printed and used per the Instructions for Use. Data collected will be recorded on the **Day 3 Laboratory Data** eCRF including:

- Date and time of evaluation
- Type of Eeva Petri Dish (number of micro-wells)

- Eeva micro-well identification
- Cell stage and Morphology grading
- Eeva results
- Number of cells after 42 hours, up to the morning of day 3
- Fate of each embryo (Transferred, Cryopreserved, Discarded or extended culture to Day 5/6)
- Eeva Petri Dish and Scope information
- Culture conditions

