14.6 Exploratory Variables

Multiple Linear regression analysis of IR (based on subject level) as dependent variable and treatment as independent parameter effected by the following confounding factors

Factors	Description
Stimulation protocol	Categorical variable, 3 states: Agonist Luteal phase; Antagonist; and Agonist Mirco-dose Flare and Other
Drugs used	Categorical variable, 3 states: recombinant Gn, urinary Gn, and mix-use of recombinant and urinary Gns
Day of transfer	Categorical variable, 2 states: D3 Vs D5/6
Age of patients	Continuous variable , years
Culture medium	Categorical variable, 5 states: Quinn's Advanced Fertilization, Global Medium, Vitro life G-IVF, Irvine Single Step Medium, and Other

A better estimate of implantation rate will be obtained based on subject level adjusted for confounding factors by a Multiple Linear regression.

Given the exploratory nature of the design, the model will be investigated stepwise and repeated backward. The final model will exclude backward P-values > 0.10.

The Center effect will also to be considered in the model.

The results of regression analysis will be reported with the following items

- Regression Coefficient with 95% CI
- Standard Error
- P-value
- Coefficient of Determination (R^2)

Subgroup analyses

Further subgroup analysis based on selected baseline parameter could be conducted as follows.

- 1) IR of the two treatment groups at each site (descriptive summary statistics with 95% CI,

and RR with 95% CI and P value). The Risk Ratio, 95% CI and P-value will be calculated, provided the number of subjects in a site will be at least 30, otherwise only descriptive statistics will be provided for that particular site.

- 2) IR, CPR, OPR and SMR of the two treatment groups for subgroups of patients with ET on D3 and D5/6 (descriptive summary statistics, RR with 95% CI and P value);
- 3) IR, CPR, OPR and SMR of the two treatment groups for subgroups of patients with age ≤35 and >35(descriptive summary statistics, RR with 95% CI and P value).
- 4) IR of the two treatment groups for subgroups of patients using 5 types of culture media (descriptive summary statistics, RR with 95% CI and P value).
- 5) IR of subgroups of patients using 5 types of culture media (regardless the method of embryo assessment, descriptive summary statistics and 95% CI)

15 Safety Evaluation

In conformity with protocol, device deficiency will be individually listed.

16 References

No reference at this stage

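### Culture medium is largely or wholly nested in centre, and SAP 14.6 does not say how the regression or the by-medium table should deal with that

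*SAP*

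**What the plan says.** On how medium is set, Protocol 5.6 states: "Culture conditions and elements will be the same for all embryos in the laboratory regardless of their allocation at randomization". Protocol 6.3.2 makes clear that the term covers media: "Culture conditions (including gas phase, media, and protein, etc". The same section leaves laboratory procedure to the site: "Oocyte retrieval and insemination will follow the standard protocol in place at each trial site".

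On the analysis, SAP 14.6 lists culture medium among the confounding factors with five states, ending in "Global Medium, Vitro life G-IVF, Irvine Single Step Medium, and Other". The stated purpose is: "A better estimate of implantation rate will be obtained based on subject level adjusted for confounding factors by a Multiple Linear regression". Terms are removed by the rule "The final model will exclude backward P-values > 0.10". Centre is covered by one sentence: "The Center effect will also to be considered in the model". The SAP does not say whether centre is fixed or random, or whether it can be removed.

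The optional subgroup list in SAP 14.6 includes two analyses by medium. Item 4 compares the arms within each medium. Item 5 pools the arms: "IR of subgroups of patients using 5 types of culture media (regardless the method of embryo assessment", with summary statistics and a 95% CI. Neither mentions centre.

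**The concern.** A factor fixed by the laboratory varies between sites, not between women within a site. The plan treats it as a covariate of the individual woman and does not mention its overlap with centre. Three consequences follow.

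- Beside fixed centre effects, a nested medium has nothing left to estimate.
- Without centre, medium is the only term that can pick up site differences, and its P value treats all women as independent.
- The by-medium rates in item 5 compare small groups of sites, yet carry intervals suited to independent women.

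At stake are the claims about media. Protocol 5.2 and 7.2 say the trial exists to generate hypotheses for later studies, so a false medium signal would be carried forward as a hypothesis.

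**Working it through.** **The plan's own figures.** The only statistical planning figures are the CI half-widths in Protocol 7.2. They follow from 1.96 × √(p(1−p)/n). At p = 0.35 this gives 4.18 points for n = 500 and 2.96 for n = 1000, against 4.2 and 3.0 in the table; the other rows also match. The formula assumes independent women. The documents give no figure for centre or medium.

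**Inputs.** About 20 sites (Protocol synopsis; section 5.1 says 22), 1500 women (Protocol 7.2), five media and the removal threshold of 0.10 (SAP 14.6). Assumed: equal site sizes (1500/20 = 75), media spread evenly (20/5 = 4 sites each), a rate of 35%, one outcome per woman, and the between-site variation stated below.

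**Step 1: estimability with fixed centre and one medium per site.**
- Columns: 1 intercept + 1 treatment + 19 centre + 4 medium = 25.
- Each medium column is a sum of site indicators, so the rank is 25 − 4 = 21 and 0 of the 4 medium contrasts are estimable.
- With age and day of transfer added, the rank is 23 of 27 (20 sites) or 25 of 29 (22 sites), again 0 of 4.
- If 1, 2, 3 or 4 suitably linked sites use two media, then 1, 2, 3 or 4 contrasts become estimable, from those sites only.
- With centre as a random effect the fixed part has full rank (6 of 6: intercept, treatment, 4 media).
- In a numerical check the treatment coefficient was 0.03777 with and without the aliased medium columns.

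**Step 2: retention of a medium with no effect.** If whole terms are tested, medium given centre has 0 degrees of freedom, while centre given medium has 19 − 4 = 15. Simulated trials (20 × 75 women, nested media, no medium effect, nominal 10%) give approximately:

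| Assumed site SD (points) | Centre never in model | Centre tested first, dropped at P > 0.10, then medium tested |
|---|---|---|
| 3 | 20% | 14% |
| 5 | 37% | 13% |
| 8 | 63% | 2% |

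In the second column the figure falls at SD 8 because centre is then kept in about 96% of trials.

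**Step 3: interval width in item 5.** With m = 75 women per site, the design effect is 1 + (m − 1) × ICC = 1 + 74 × ICC. The unadjusted interval has 1/√(design effect) of its proper width. At a rate of 35%, ICC = SD²/(0.35 × 0.65) = SD²/0.2275. An SD of 3 points gives 0.0009/0.2275 = 0.004, and 8 points gives 0.0064/0.2275 = 0.028.

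| Assumed ICC | Design effect | Share of proper width |
|---|---|---|
| 0.004 | 1.30 | 88% |
| 0.01 | 1.74 | 76% |
| 0.028 | 3.07 | 57% |
| 0.05 | 4.70 | 46% |

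In points, a medium used at 4 sites has 4 × 75 = 300 women. The unadjusted half-width is 1.96 × √(0.2275/300) = 5.4 points. The proper one is 5.4 × √1.30 = 6.2 points at ICC 0.004 and 5.4 × √4.70 = 11.7 points at ICC 0.05.

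**The case against.** The strongest reply is that nesting is inferred. The sentence in Protocol 5.6 mainly assures the reader that the two arms are cultured alike. No passage says that a site keeps one medium throughout the trial. Media are recorded for each subject, and the SAP lists the medium as a patient variable (section 17) and tabulates it by arm (section 19.2.5). Centre could also be a random effect. This stands: exact aliasing is conditional on one medium per site and fixed centre effects. It does not close the gap, because even with a few two-medium sites or a random centre effect, information on media comes from few sites, and the SAP does not say which case applies.

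A reader might also infer that the arm comparison is compromised. It is not: the aliased columns leave the treatment coefficient unchanged, and the primary analysis in SAP 14.1 contains no regression.

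A reader might infer that the selection procedure keeps medium or centre arbitrarily. That would happen with column-by-column removal. With whole-term testing, centre can be tested given medium, and the retention rates are those in the second column of the Step 2 table. The higher rates apply only if centre is never in the model.

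Item 4 might seem to share the fault. It compares arms within a medium, so it does not itself turn site differences into medium effects.

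Finally, item 5 is optional and descriptive, with no P value, and item 1 already shows rates by site. That limits the importance of the point but does not make the item 5 intervals right.

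**Conclusion.** The concern holds in a limited form. The protocol implies that medium is a laboratory-level condition, and SAP 14.6 analyses it as a characteristic of the woman without settling the role of centre. With one medium per site and fixed centre effects, no medium contrast is estimable. If centre is absent, a null medium is retained about two to six times as often as the nominal 10%. If centre is tested first, the excess is small (about 14% and 13% at SDs of 3 and 5 points) and disappears at 8 points. Item 5 intervals have about 88% to 46% of proper width for an ICC of 0.004 to 0.05.

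The site SDs, ICCs, 35% rate, equal site sizes and even spread of media are assumptions; the documents give no between-site variation. The documents do not support saying that medium is unidentifiable in every case, that the treatment estimate is affected, or that medium must be discarded outright.

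**What to change.** In SAP 14.6:

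1. Force centre into the regression, exempt from removal at P > 0.10, and state whether it is fixed or random.
2. Tabulate medium by site before fitting. Where medium is nested, leave it out of a fixed-centre model, or use a random centre effect and report the number of sites per medium.
3. Give item 5 site-clustered confidence intervals and label it a between-site description that cannot separate medium from site.

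Item 4 needs no change on this ground. The cost is SAP wording, one table and a model option. The price in results is wider intervals and little or no separate claim about media, which the design could hardly support anyway.

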7.14	Data Monitoring Committee.....	29
8	Ethical and Regulatory Aspects.....	29
8.1	Responsibilities of the Investigator	29
8.2	Subject Information and Informed Consent	30

8.3	Subject Identification and Privacy.....	31
8.4	Independent Ethics Committee or Institutional Review Board	31
8.5	Health Authorities.....	32
9	Trial Management.....	32
9.1	Electronic Case Report Form Handling.....	32
9.2	Source Data and Subject Files	32
9.3	Investigator Site File and Archiving.....	33
9.4	Monitoring, Quality Assurance and Inspection by Health Authorities	33
9.5	Assessment of Clinical Investigators and Sites	33
9.6	Trial Training.....	34
9.7	Required Trial Equipment	34
9.8	Site Activation and Supply of Trial Materials.....	35
9.9	Changes to the Clinical Trial Protocol.....	35
9.9.1	Clinical Trial Report.....	35
9.10	Publication	36
10	Intellectual Property.....	36
11	Trial or site Discontinuation	37
12	Trial Closure	37
13	References.....	37

List of Abbreviations

AE	Adverse Event
AFC	Antral Follicular Count
AMH	Antimullerian Hormone
ART	Assisted Reproductive Technologies
B	Blastocyst
CE	European Community
CRF	Case Report Form
CRO	Contract Research Organization
CSL	Clinical Science Liaison
EB	Early Blastocyst
EC	Ethics Committee
eCRF	Electronic Case Report Forms
EDC	Electronic Data Capture
EEVA H/M/L	Eeva Predicted High, M: Medium, L: Low
ET	Embryo Transfer
EU	European Union
GP	General Practitioner
hCG	Human Chorionic Gonadotropin
HFEA	Human Fertilisation and Embryology Authority – UK
ICF	Informed Consent Form
ICH	International Committee on Harmonisation
ICSI	Intracytoplasmatic Sperm Injection
IEC	Independent Ethics Committee
INN	International Nonproprietary Name
IRB	Institutional Review Board

ITT	Intention to Treat
IVF	In Vitro Fertilization
NCA	National Competent Authorities
PN	Pronuclei stage
SAP	Statistical Analysis Plan
SPC	Summary of Product Characteristics
USA	United States of America

1 Synopsis

Trial title	A Phase IV, prospective, randomized, exploratory, multicenter, Eeva trial (Time Lapse Eeva – TiLE)
Trial number	EMR700623 545
Sponsor	Merck KGaA, [name]
Trial type	Prospective, randomized, multicenter Trial
Coordinating Investigator	PPD
Trial center(s)/country(ies)	Approximately 20 Centers in 8 Countries: Canada, Germany, Italy, France, Norway, Sweden, Spain, UK
Planned Trial period	April 2015 – March 2017

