5.1 Overall Trial Design and Plan

In general, the Eeva EU/Canadian trial will include 22 investigational sites. Each site will conduct the trial using the same clinical protocol.

Recruitment of patients at each site, with subjects who voluntarily consent to participate, is expected to continue for up to 9 months. Additional follow-up after embryo transfer will take place up to Day 12-18 days to verify biochemical pregnancy and at 5-8 gestational weeks to verify clinical pregnancy. Additionally, pregnancy outcomes will be collected via eCRF for subjects who were pregnant at the 5-8 week gestational follow-up visit (or subsequent ultrasound results). Total duration of the trial, including start up and close out activities, is approximately 19 months. Desired follow-up endpoints and additional collection of outcomes like spontaneous miscarriage is not being considered in the timeline for completion.

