14.2 Implantation rate in other selections

The point estimate and 95% CI of IR and IR^* will be calculated in the subgroups EC and ENC. No tests of comparison between any subgroup will be conducted.

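### SAP 14.6 plans P values for Eeva versus control inside each subgroup level, but no estimate of whether the effect differs between levels

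*SAP*

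**What the plan says.** SAP 14.6 opens its subgroup list with "Further subgroup analysis based on selected baseline parameter could be conducted as follows". Items 1 to 4 then ask for EMG against MG within strata:

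- **Site**, implantation rate (IR) only: "The Risk Ratio, 95% CI and P-value will be calculated, provided the number of subjects in a site will be at least 30". Smaller sites get descriptive statistics.
- **Transfer day**, four outcomes (IR, clinical pregnancy, ongoing pregnancy, miscarriage): "ET on D3 and D5/6 (descriptive summary statistics, RR with 95% CI and P value".
- **Age**, the same four outcomes: "IR, CPR, OPR and SMR of the two treatment groups for subgroups of patients with age ≤35 and >35", again with RR, CI and P value.
- **Culture medium**, five types, IR only, with RR, CI and P value.

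Item 5 (media regardless of arm) has no P value.

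The regression earlier in 14.6 contains treatment, five covariates and a center effect. It names no treatment-by-factor term. Neither document gives a heterogeneity estimate, a multiplicity rule or a rule for interpreting the subgroup P values.

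The number of sites differs within the protocol. The synopsis has "Approximately 20 Centers in 8 Countries", while section 5.1 says "the Eeva EU/Canadian trial will include 22 investigational sites".

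**The concern.** A subgroup analysis by arm is meant to show whether the treatment effect changes across levels of a factor. A set of separate within-level P values does not show this. Each one depends on the size of its stratum as well as on the effect, so an identical effect can easily be significant in one level and not in the next.

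Protocol 5.2 and 7.2 say the trial is to generate hypotheses for later confirmatory work. What such a trial needs from its subgroups is an estimate of how much the effect varies by age, laboratory conditions or centre. The plan gives that estimate no place and offers a list of P values, from which a chance result in one age band, medium or site could be carried forward as a lead.

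**Working it through.** **Inputs from the documents.** 1000 EMG and 500 MG subjects, 2:1 (protocol 7.2, 7.3); 20 or 22 sites (synopsis, 5.1); strata and outcomes as listed in SAP 14.6.

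**Assumptions.** Two-sided 0.05 per test (no level is stated), one binary outcome per woman, and the event rates and age splits given below.

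**The plan's own figure.** The documents give no count of P values. Their one design figure is the CI table in protocol 7.2. It reproduces in all ten cells with 1.96 × √(p(1−p)/n); for example, 30% gives 4.02 points at n = 500 and 2.84 at n = 1000. It describes whole-arm precision only.

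**1. Same effect in both age bands.** Power per band = Φ(Δ/SE − 1.96), with SE = √(p₁(1−p₁)/n₁ + p₀(1−p₀)/n₀). Take 30% in MG, 35% in EMG and a 60/40 age split.

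- 600 vs 300: SE = √(0.2275/600 + 0.21/300) = 0.0329; 0.05/SE = 1.52; power 0.331.
- 400 vs 200: SE = √(0.2275/400 + 0.21/200) = 0.0402; 0.05/SE = 1.24; power 0.237.
- Exactly one band significant: 0.331 × 0.763 + 0.237 × 0.669 = 0.41.

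The age split matters little: splits from 50/50 to 70/30 give 41% to 42%. With 35% against 42% and a 60/40 split the figure is 51%.

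**2. Compared with a heterogeneity test.** Simulation: N = 1500, 2:1, log-RR Wald tests within strata, Cochran's Q between strata, equal strata, same rates in every stratum.

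| Strata | MG vs EMG rate | Some but not all strata significant | Q rejects |
|---|---|---|---|
| 2 | 35% vs 35% | 9% | 5% |
| 2 | 35% vs 40% | 37% | 5% |
| 5 | 35% vs 35% | 22% | 4% |
| 5 | 35% vs 40% | 45% | 5% |

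With 20 equal sites and no effect, at least one site is significant in 55% of trials. Q rejects in about 2%, so it is conservative for strata this small.

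**3. Number of P values.** Sites × 1 + transfer day 2 × 4 + age 2 × 4 + medium 5 × 1.

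| Qualifying sites | P values | Expected below 0.05, no effect | At least one, if independent |
|---|---|---|---|
| 0 | 21 | 1.05 | 66% |
| 10 | 31 | 1.55 | 80% |
| 20 | 41 | 2.05 | 88% |
| 22 | 43 | 2.15 | 89% |

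The tests share women and outcomes, so independence overstates the last column. A joint simulation of the 41 tests gives about 78% (20 equal sites, rate 35%, miscarriage 15% of pregnancies, one embryo per woman so that IR and clinical pregnancy coincide). If both IR definitions of SAP 14.1 were used, the count would be 70 with 20 sites or 74 with 22.

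**4. Site precision.** The threshold counts both arms, so 30 women at 2:1 are about 20 vs 10. At an assumed 35%:

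- 20 vs 10: SE(log RR) = √((0.65/0.35)(1/20 + 1/10)) = 0.528; the interval around RR = 1 is 0.36 to 2.81.
- Average site, 1500/20 = 75, or 50 vs 25: SE = 0.334. The expected extreme of 20 standard normals is 1.87, so with no true difference the lowest and highest of 20 site RRs are expected near exp(±0.623), or 0.54 and 1.87.

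**5. Transfer day.** Enrolment is decided on day 1 (protocol 8.2). Day 2 grading is already restricted by randomized group (6.3.2). Eeva results are used on Day 3, when each embryo's fate, including extended culture, is recorded (6.3.3). Transfer day therefore follows randomization and can depend on arm, although 14.6 groups it with baseline parameters.

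**The case against.** The SAP attaches no threshold or claim to these P values. The analyses are optional, sit in an exploratory section, and feed hypotheses that later trials are meant to test. Small sites are already excluded from testing, and a center effect is considered in the regression. Each stratum RR comes with a CI, so for the two-level factors a reader could derive the ratio of RRs.

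Much of this stands. It bars the reading that chance patterns *will* be taken for effect modification: the documents draw no such conclusion, so *can* is as far as the text goes. Nor is the information lost for age; the gap there is that the estimate is not planned or reported. The multiplicity figures and the missing interaction estimate are also separate arguments. Only steps 1 and 2 bear directly on the second.

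A reader might also take the sentence in SAP 14.2, "No tests of comparison between any subgroup will be conducted", as contradicting 14.6. It belongs to the comparison of Eeva-conform and non-conform subjects, so it does not govern the age, day, medium or site strata. SAP 14.1 does rule out inferential comparison of EMG and MG in the ITT selection as the study is descriptive, and then labels later sections secondary. That sits awkwardly with P values for the same two groups in 14.6, but it is a separate question of consistency.

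The exploratory label does not answer the main point. Generating hypotheses is the trial's purpose, and a main-effect center term does not measure variation of the treatment effect between centres.

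**Conclusion.** The concern holds in this form: 14.6 asks for within-stratum P values and plans no estimate of effect differences between strata. Under a uniform effect of 30% to 35%, one age band but not the other is significant in about 41% of trials. This rests on assumed rates, a 0.05 level and one binary outcome per woman; it hardly changes with the age split.

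The expected number of false positives with no effect is about 1 to 2. A reader might settle on 41 tests and 88% as the headline. The documents do not fix those figures: they need 20 sites that all reach 30 subjects, and independent tests. The supported range is 21 to 43 P values, with 66% to 89% under independence and less with overlap.

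The primary estimates are not affected. This is a worthwhile improvement to a secondary, optional part of the plan.

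**What to change.** In SAP 14.6:

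- **Age:** replace the within-band P values by one ratio of RRs with 95% CI per outcome: exp[(log RR₁ − log RR₂) ± 1.96√(SE₁² + SE₂²)]. Show band RRs with CIs only. Where more than one embryo is transferred, the SEs for IR should allow for clustering within women.
- **Culture medium:** one heterogeneity estimate for IR across the five types, and stratum RRs with CIs only.
- **Site:** replace the site-by-site P values and the 30-subject rule by a centre-stratified RR (Mantel-Haenszel, for example) and one between-centre heterogeneity estimate.
- **Transfer day:** drop the P values and label the results descriptive, because day is decided after randomization.

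This leaves 4 + 1 + 1 = 6 effect-difference estimates in place of up to 41 to 43 P values. The analyses may stay optional.

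The cost is SAP wording and a few lines of code, with no new data. The intervals will be wide. With a 60/40 age split and 30% vs 35%, the variance of the log ratio is (0.65/210 + 0.70/90) + (0.65/140 + 0.70/60) = 0.0272, so SE = 0.165 and the CI around a ratio of 1 runs from 0.72 to 1.38. Fewer subgroup results will look positive, but the interval shows what the trial can say about effect modification.

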8.2 Subject Information and Informed Consent

An unconditional prerequisite for a subject's participation in the trial is his/her written informed consent.

To protect the rights and welfare of trial subjects, the trial will be conducted in conformance with the Declaration of Helsinki and elements of good clinical practices as may be applied to medical devices.^{1,2} The confidentiality provisions within all applicable laws and regulations will apply throughout. Obtaining informed consent in accordance with the policy of the EC, this clinical protocol, and applicable regulations is mandatory for subject participation. The sponsor will avoid improper influence on or inducement of the subject for participating in the trial. The subject informed consent document(s) must be provided in a language that the patient reads and understands. All subjects must provide voluntary, written informed consent prior to the start of any trial-related activities. This includes subjects who are the partners of the subjects, if applicable.

Informed consent should be signed prior to the day of oocyte pick up, preferably on the day of the last ultrasonography for assessment of number of follicles available. On day 1 after oocyte pick up and following assessment of the number of 2PNs available, subjects will either be enrolled in the trial or not included in the trial.

Adequate information must therefore be given to the subject by the Investigator before informed consent is obtained (a person designated by the Investigator may give the information, if permitted by local regulations). A subject information sheet in the local language will be provided by the Sponsor for the purpose of obtaining informed consent. In addition to providing this written information to a potential subject, the Investigator or his/her designee will inform the subject verbally of all pertinent aspects of the trial (*the language used in doing so must be chosen so that the information can be fully and readily understood by laypersons*). Depending on national regulations, a person other than the Investigator may inform the subject and sign the Informed Consent Form.

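### The SAP 14.6 between-arm regression adjusts for day of transfer, and calls the D3 and D5/6 strata baseline subgroups, although the day is recorded after enrolment and the arm may influence it

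*SAP*

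**What the plan says.** SAP 14.6 plans a "Multiple Linear regression analysis of IR (based on subject level) as dependent variable and treatment as independent parameter", adjusted for five listed confounding factors. One is day of transfer: "Categorical variable, 2 states: D3 Vs D5/6". Centre is also to be considered. Terms are selected stepwise and backward: "The final model will exclude backward P-values > 0.10".

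The same section introduces its subgroups with "Further subgroup analysis based on selected baseline parameter could be conducted as follows". Item 2 is "IR, CPR, OPR and SMR of the two treatment groups for subgroups of patients with ET on D3 and D5/6", with risk ratios, confidence intervals and P values.

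On timing, Protocol 8.2 says: "On day 1 after oocyte pick up and following assessment of the number of 2PNs available, subjects will either be enrolled in the trial". Protocol 6.3.3 says of Day 3 that "Eeva results will be printed and used per the Instructions for Use". The form completed on that day also records "Fate of each embryo (Transferred, Cryopreserved, Discarded or extended culture to Day 5/6".

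SAP 14.1 rules out inferential comparison of the arms in the primary analysis. Protocol 7.5 and SAP 8.1 group subjects by the method used rather than as randomised.

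**The concern.** A confounder in a randomised comparison should be fixed before allocation. Day of transfer is not shown to be: enrolment is on day 1, the choice to transfer or extend culture is recorded on Day 3, and by then the Eeva result is known in one arm only of an unblinded trial. No section fixes the day before randomisation.

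There is a plausible route from arm to day. Protocol 3.1.2 describes Eeva as forecasting blastocyst formation at cleavage stage, and SAP 8.2 bases selection for transfer in the Eeva arm on its recommendation. If Eeva changes who is transferred on which day, two things follow. Women in the same day stratum no longer have the same prognosis in both arms. And any Eeva effect that acts through the day is adjusted away.

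This matters because the regression is the only whole-trial between-arm model in the SAP, in a trial meant to generate hypotheses for later confirmatory work. The report might also not reveal a problem. Day is collected (SAP 5.4.4), but the tables in SAP 19.2.6 include none of day by arm.

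**Working it through.** **1. The plan's own figure.** The only design calculation is the precision table in Protocol 7.2. At a 35% rate, 1.96 × √(0.35 × 0.65 / n) gives 4.18 points for n = 500 and 2.96 for n = 1000; the table prints 4.2 and 3.0. The other entries also reproduce. The table does not decide this point, but it sets the scale:
- SE of the arm difference: √(0.35 × 0.65 × (1/1000 + 1/500)) = 2.61 points.
- SE within a day stratum, if half of each arm falls in it: √(0.35 × 0.65 × (1/500 + 1/250)) = 3.7 points.

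**2. Assumed model.** The documents give no figures for the share transferred on Day 5, its link to prognosis, or the effect of day. All of the following is assumed:
- single transfers, 1000 Eeva and 500 control subjects;
- unmeasured prognosis q ~ N(0,1);
- implantation logit −0.65 + 0.5q (about 35%), with no true arm effect within a day;
- control Day 5 logit 0.5q;
- least-squares regression of outcome on arm and day, evaluated by numerical integration.

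**3. Arm does not affect day.** Bias is 0 and type I error 5.0%.

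**4. Eeva raises the Day 5 share; day itself has no effect.**

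| Rise in Day 5 share | Adjusted coefficient | In SE units | Type I error |
|---|---|---|---|
| 5 points | −0.3 points | 0.1 | 5.1% |
| 9 points | −0.5 | 0.2 | 5.4% |
| 22 points | −1.1 | 0.4 | 7.0% |

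The SE is 2.6 to 2.7 throughout. A second set of assumed inputs (Day 5 share 50% in control, 60 to 72% with Eeva) gave −0.2 to −1.6 points.

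**5. Same Day 5 share, but Eeva sorts women by prognosis more sharply** (slope on q above the control value of 0.5). The adjusted coefficient stays at 0, but the strata move apart:

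| Eeva slope | D3 stratum | D5 stratum | Type I error per stratum |
|---|---|---|---|
| 0.75 | −1.1 points | +1.1 points | about 6% |
| 1.0 | −1.9 | +1.9 | about 8% |
| 1.5 | −3.2 | +3.2 | about 14% |

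The SEs are 3.6 and 3.8. The pattern would look like an Eeva-by-day interaction where none exists. With both mechanisms (+8 points, slope 1.0), the coefficient is −0.6 and the strata −2.6 and +1.2.

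**6. Day 5 transfer itself implants about 10 points better.** The share shifts in step 4 then create a real total Eeva difference of about 0.10 × 5 = 0.5, 0.10 × 9 = 0.9 and 0.10 × 22 = 2.2 points. The day-adjusted coefficients are −0.3, −0.5 and −1.2. They miss the total by 0.8, 1.4 and 3.4 points (0.3, 0.5 and 1.2 SE), with the sign reversed.

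**7. The P > 0.10 rule, if it were applied to treatment.** The cut-off is 1.645 × 2.61 = 4.30 points. A true 3-point effect would be kept with probability Φ((3 − 4.30)/2.61) + Φ((−4.30 − 3)/2.61) ≈ 31%, and would average 5.9 points when kept.

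**8. Precision lost by dropping day.** The share of variance due to day, with half the subjects on each day, is 0.25 × d² / (0.35 × 0.65). For d = 5, 10 and 15 points this is 0.27%, 1.10% and 2.47%. Dividing by √(1 − R²), the SE rises by 0.14%, 0.55% and 1.26%.

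**The case against.** The strongest reply is that no harm is shown. A reader might infer that Eeva alters the day of transfer and that the regression is therefore biased. The documents do not support this. Protocol 6.3.4 leaves transfer to each site's standard, and Protocol 8.1 has the investigator decide the strategy in advance. Where site policy sets the day, day is partly a marker of site. This stands: the bias is conditional, and zero if the arm does not move the day. Yet neither section mentions day of transfer, so neither makes it a pre-randomisation variable.

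The sizes are also modest, and come from a model that lets neither age nor centre absorb prognosis and that always keeps day. Under the SAP's own P > 0.10 rule, day would be kept only 61 to 66% of the time where it has no effect. In one such case the mean coefficient falls from −1.17 to −0.96, with type I error essentially unchanged. The 14% figure needs a slope three times that of control. This stands too.

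A day-specific result has some interest, since the primary objective covers Day 3/5 transfers. That supports reporting it as a labelled sensitivity result, not as the main adjusted estimate.

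SAP 11.2 promises tables by arm for post-baseline variables, but refers to section 19, where day does not appear. Day could be derived from the per-patient listings (SAP 19.1 and 19.2.10), so it is not hidden, only untabulated.

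A reader might also infer that the SAP will drop treatment at P > 0.10. It names treatment apart from the confounders, so keeping it may well be intended. This is an ambiguity of wording and would not carry a point alone.

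**Conclusion.** The point holds in a limited form. SAP 14.6 conditions its only whole-trial between-arm model on a variable recorded after enrolment, and labels strata of that variable as baseline. Whether this biases anything depends on the arm affecting the day, which the documents neither show nor exclude. If it does, with no true arm or day effect, the assumed cases give about 0.3 to 1.1 points of bias in the coefficient (0.1 to 0.4 SE) and up to about 3 points in the strata (under 1 SE). The larger discrepancy, up to 3.4 points with the sign reversed, needs a 22-point shift in share and a 10-point day effect together.

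It would be tempting to conclude that removing day restores a randomised comparison. It does not by itself, because subjects are grouped by method used.

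The section is exploratory, the subgroups are optional, and the descriptive estimates in SAP 14.1 are untouched. This is a cheap improvement, not a flaw in the primary result.

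**What to change.** - Leave day of transfer out of the main treatment-effect model. If a day-adjusted coefficient is wanted, report it only as a labelled sensitivity result.
- Relabel the D3 and D5/6 results as post-randomisation descriptive subsets without between-arm P values, and add a table of transfer day by arm to SAP 19.2.6.
- As a minor clarification, state that treatment is always kept and that the P > 0.10 rule applies only to the listed factors.
- Run the regression with arms as randomised if its coefficient is to be read as a randomised contrast.

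Culture medium may stay in the model, because Protocol 5.6 makes culture conditions the same regardless of allocation.

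The cost is SAP wording, one table from data already collected, the loss of up to 8 optional P values (4 outcomes × 2 strata), and a rise in SE of about 0.1 to 1.3% if Day 3 and Day 5 rates differ by 5 to 15 points (assumed).
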